9.4.6.3. Hypertension

Patients who experience changes in BP (systolic BP at ≥ 160 mm Hg plus ≥ 20 mm Hg increase from baseline [Week 0; Visit 2]; and/or diastolic BP at ≥ 100 mm Hg plus ≥ 10 mm Hg increase from baseline) on 2 consecutive visits should receive intervention for the management of hypertension. Intervention could include the maximal intervention of withholding the dose of investigational product and/or the introduction of an anti-hypertensive agent.

9.4.6.4. Allergic Reactions and Hypersensitivity Events

All biologic agents carry the risk of systemic allergic/hypersensitivity reactions. Clinical manifestations of these reactions may include but are not limited to:

- Skin rash
- Pruritus (itching)
- Dyspnea
- Urticarial (hives)
- Angioedema (for example, swelling of the lips and/or tongue)
- Hypotension
- Anaphylactic reaction

Participants with clinical manifestations of systemic allergic/hypersensitivity reactions should be treated per local standard of care. Additional data describing each symptom should be provided to the sponsor in the CRF.

In case of anaphylaxis or generalized urticaria, additional blood samples should be collected as close as possible to the onset of the event (see Section 9.4.4 Immunogenicity Assessments). Follow-up samples should be obtained at the next regularly scheduled visit or 4 weeks after the event, whichever is later. The lab results are provided to the sponsor via the central laboratory.

9.5. Pharmacokinetics

Not applicable

9.6. Pharmacodynamics

Not applicable

9.7. Whole Blood Samples for Pharmacogenetic Research

A whole blood sample will be collected for pharmacogenetic analysis as specified in the Schedule of Activities (Section 2) where local regulations allow.

Samples will not be used to conduct unspecified disease or population genetic research either now or in the future. Samples will be used to investigate variable response to ixekizumab and to investigate genetic variants thought to play a role in GPP and EP. Assessment of variable response may include evaluation of AEs or differences in efficacy.

All samples will be coded with the patient/number. These samples and any data generated can be linked back to the patient only by the investigator site personnel. Samples will be retained at a facility selected by Eli Lilly Japan or its designee for a maximum of 15 years after the last patient visit for the study, or for a shorter period if local regulations and/or ERBs/IRBs impose shorter time limits.

Molecular technologies are expected to improve during the 15-year storage period and therefore cannot be specifically named. However, existing approaches include whole genome or exome sequencing, genome wide association studies, and candidate gene studies. Regardless of technology utilized genotyping data generated will be used only for the specific research scope described in this section.

9.8. Biomarkers

Not applicable

9.9. Health Outcomes/Quality of Life Assessment

The following health outcomes measures that will be assessed in this study:

- Itch Numeric Rating Scale (NRS)
- Dermatology Life Quality Index (DLQI)

9.9.1. Itch Numeric Rating Scale

The Itch NRS is a patient-administered, 11-point horizontal scale anchored at 0 and 10, with 0 representing “no itch” and 10 representing “worst itch imaginable.” Overall severity of a patient's itching from Ps is indicated by circling the number that best describes the worst level of itching in the past 24 hours.

9.9.2. Dermatology Life Quality Index

The DLQI is a simple, patient-administered, 10-question, validated, quality-of-life questionnaire that covers 6 domains, including symptoms and feelings, daily activities, leisure, work and school, personal relationships, and treatment. Response categories include “not at all”, “a little”, “a lot”, and “very much”, with corresponding scores of 0, 1, 2, and 3, respectively, and unanswered (“not relevant”) responses scored as “0.” Totals range from 0 to 30 (the higher the score, the more quality of life is impaired) and a 5-point change from baseline is considered clinically relevant (Basra et al. 2008).

10. Statistical Considerations

10.1. Sample Size Determination

A total of 12 patients will be enrolled so that at least 5 patients with EP and 5 patients with GPP who are inadequate responders ($\text{GIS} \geq 2$ at Week 12 and based on investigators' discretion) will continue to use ixekizumab beyond Week 12. Additional enrollment may occur and the sample size may be increased, if no GPP or EP patients enter into Period 3 (Maintenance Dosing Period) of the study.

The sample size is based on the following:

- In the I1F-JE-RHAT (RHAT) study, 5 GPP and 8 EP patients were enrolled. One GPP patient achieved $\text{GIS} = 1$ (resolved) at Week 12 and the other 4 GPP patients achieved $\text{GIS} = 2$ (improved). One EP patient achieved $\text{GIS} = 1$ at Week 12 and 7 EP patients achieved $\text{GIS} = 2$. Although the sample size is very small, based on the result of RHAT study, it is assumed that approximately 5 patients at maximum may not achieve $\text{GIS} = 1$ at Week 12 and may continue ixekizumab Q2W beyond Week 12 based on the investigators' discretion.
- The sample size is determined based on the feasibility in Japan. The prevalence rate of these patients is very low in Japan and it is also difficult to conduct a placebo-controlled study for these severe conditions (Umezawa et al. 2003, Rosenbach et al. 2010).

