5.2. Number of Participants

A total of 12 patients will be enrolled so that at least 5 patients with EP and 5 patients with GPP who are inadequate responders (GIS ≥ 2 at Week 12 and based on the investigators' discretion), will continue to use ixekizumab beyond Week 12. Additional enrollment may occur and sample size may be increased, if no GPP or EP patients enter into Period 3 (Maintenance Dosing Period) of the study.

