10.2. Populations for Analyses

For purposes of analysis, the following populations are defined:

Efficacy, health outcomes and safety analyses for Period 2 will be conducted on the largest analysis set (Full Analysis Set [FAS]), defined as the set of patients with GPP and EP separately who receive at least 1 dose of study treatment in Period 2 (FAS Population).

Efficacy, health outcomes and safety analyses for Period 3 will be conducted based on patients with GPP and EP separately who receive at least 1 dose of study treatment in Period 3 (Maintenance Dosing Period Population).

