10.3. Statistical Analyses

10.3.1. General Statistical Considerations

Statistical analysis of this study will be the responsibility of Eli Lilly Japan.

Any change to the data analysis methods described in the protocol will require an amendment ONLY if it changes a principal feature of the protocol. Any other change to the data analysis methods described in the protocol, and the justification for making the change, will be described in the clinical study report (CSR). Additional exploratory analyses of the data will be conducted as deemed appropriate.

Primary analysis of efficacy, health outcome, and safety measures will be conducted based on patients who continued ixekizumab 80 mg Q2W beyond Week 12 by disease type (ie, GPP and

EP separately) on the Maintenance Dosing Period Population. Secondary analyses of efficacy, health outcome, and safety measures will be conducted for Period 2 on the FAS Population and Period 3 on the Maintenance Dosing Period Population, respectively.

Baseline for efficacy, health outcomes, and safety analyses in Period 2 is defined as the last available value before first dose in Period 2; in most cases, it will be the value recorded at Week 0 (Visit 2). For the efficacy and health outcomes analyses in Period 3, baseline is defined as the last available value before the first dose in Period 2 and, in most cases, will be the value recorded at Week 0 (Visit 2). Unless otherwise specified, for the safety analyses during Period 3, baseline is defined as the last available value before the first dose of ixekizumab in Period 3. In most cases, this will be the measure recorded at Week 12 (Visit 6).

As this is a single arm study with very small sample size, no statistical inference will be performed.

Continuous data will be summarized in terms of the mean, standard deviation, minimum, maximum, median, and number of observations. Categorical data will be summarized as frequency counts.

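### The sample-size rationale makes 5 continuing patients per disease both a minimum and a maximum, and 12 enrolled supports 5 only as an average

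*Protocol*

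**What the plan says.** The size statement appears in the Protocol synopsis, Protocol 5.2, Protocol 10.1 and SAP 5.2. In each place it begins "A total of 12 patients will be enrolled so that at least 5 patients with EP and 5 patients with GPP", all of them inadequate responders, will stay on treatment after Week 12. Continuing requires GIS ≥ 2 at Week 12 and also depends on the investigator's discretion.

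Protocol 10.1 and SAP 5.2 add two supporting arguments that the synopsis and Protocol 5.2 do not print:

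- **RHAT results.** One of 5 GPP patients and 1 of 8 EP patients were resolved (GIS = 1) at Week 12; the other 4 and 7 were at GIS = 2. The text continues "Although the sample size is very small, based on the result of RHAT study", and then "it is assumed that approximately 5 patients at maximum may not achieve" GIS = 1 and may continue, again at the investigator's discretion. It does not say whether this 5 is per disease or in total.
- **Feasibility.** "The sample size is determined based on the feasibility in Japan".

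The size statement is followed in all four places by a clause on further recruitment. In Protocol 5.2 it reads: "Additional enrollment may occur and sample size may be increased, if no GPP or EP patients enter into Period 3". Neither document gives a planned split of the 12 between GPP and EP, or a quota for either.

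**The concern.** The first sentence of the rationale offers 5 per disease as the least that 12 enrolled patients should yield. The bullet meant to support it offers 5 as the most that may continue. Both cannot describe the same quantity, and the reader is not told which applies.

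The figure describes the group from which the primary result is counted. Protocol 10.2 defines the Period 3 population as "patients with GPP and EP separately who receive at least 1 dose of study treatment in Period 3", and the primary endpoint is a count within it, by disease. The study is run to meet a regulatory commitment on dosing beyond Week 12 in these two diseases. The number expected to provide that evidence should therefore be described accurately.

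**Working it through.** **Inputs.** From Protocol 10.1 and SAP 5.2: 12 enrolled; target 5 per disease; RHAT proportion not at GIS = 1 at Week 12 of 4/5 = 0.80 (GPP) and 7/8 = 0.875 (EP). Assumed, because the documents do not say: the split of the 12, and that every patient with GIS ≥ 2 at Week 12 continues.

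**Step 1: reproduce the 12.** Number to enrol for 5 continuers on average = 5 / rate.

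- GPP: 5/0.80 = 6.25
- EP: 5/0.875 = 5.71
- Sum: 11.96, which rounds to 12

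The documents do not show this derivation, but 12 agrees with it. It is a calculation of averages. In whole patients, an average of 5 in both diseases needs 7 GPP and 6 EP, or 13. No whole-number split of 12 achieves it.

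**Step 2: chance of at least 5 in both.** With n enrolled in a disease and rate p, the expected number is n × p and the chance of at least 5 is the binomial upper tail. The joint chance is the product of the two. At 6 + 6:

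- GPP: 6 × 0.80⁵ × 0.20 + 0.80⁶ = 0.393 + 0.262 = 0.655
- EP: 6 × 0.875⁵ × 0.125 + 0.875⁶ = 0.385 + 0.449 = 0.833
- Both: 0.655 × 0.833 = 0.546

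| Split (GPP + EP) | Expected GPP / EP | P(GPP ≥ 5) | P(EP ≥ 5) | P(both ≥ 5) |
|---|---|---|---|---|
| 6 + 6 | 4.80 / 5.25 | 0.655 | 0.833 | 0.55 |
| 5 + 7 | 4.00 / 6.13 | 0.328 | 0.954 | 0.31 |
| 7 + 5 | 5.60 / 4.38 | 0.852 | 0.513 | 0.44 |
| any other | n/a | n/a | n/a | 0 |

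The last row is zero because one disease then has fewer than 5 patients enrolled.

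**Step 3: sensitivity.** If 90% of unresolved patients continue (an assumption), the rates become 0.72 and 0.7875 and the three joint chances fall to 0.29, 0.16 and 0.21. With full continuation at 6 + 6, rates of 0.70/0.80 give 0.28 and rates of 0.90/0.90 give 0.78.

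**Step 4: is 5 a maximum?**

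- *Per disease.* At 6 + 6 as many as 6 could continue. The chance that all 6 do so in at least one disease is 1 − (1 − 0.262)(1 − 0.449) = 0.59.
- *In total.* A ceiling of 5 contradicts the target of 10 and RHAT's 11 of 13. The expected total is 12 × 11/13 = 10.2, and at 6 + 6 the chance of 5 or fewer is about 0.001.

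**Step 5: does the recruitment clause protect the target?** Its stated condition is that no GPP or EP patients enter Period 3. At 6 + 6 the chance of none is 0.20⁶ = 0.00006 for GPP and 0.125⁶ = 0.000004 for EP. Almost all of the 1 − 0.55 = 0.45 chance of missing the target comes from one to four continuers in a disease, which does not meet that condition.

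**The case against.** The strongest reply is that the size sentence states an aim, not a guarantee, and that 12 reproduces as a sensible average. The shortfall for GPP at 6 + 6 is 0.2 of a patient, on a rate taken from 5 patients. The rationale is openly tentative. In all four places the next sentence allows for no patients of a disease entering Period 3, and the synopsis itself calls the sample very small. This stands, and it keeps the point small. A reader might infer that the synopsis and Protocol 5.2 promise 5 per disease and conceal the uncertainty. Those cautions do not support that, although the remarks on RHAT and feasibility are absent there.

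The ceiling can also be read kindly. Before discretion about 5 per disease are expected, and discretion only removes patients, so 5 is roughly the most to expect. That is plausible, but it makes a minimum of 5 less supported, so the two sentences still clash.

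A reader might go further and infer that the study is underpowered or that 12 is a computational error. The documents do not support this. Protocol 10.3.1 says: "As this is a single arm study with very small sample size, no statistical inference will be performed". There is no power to lose. Period 3 is analysed on whoever is dosed, and SAP 6.7 reports Period 3 disposition by disease.

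**Conclusion.** The point holds as a minor inconsistency. The same 5 is a minimum in the size statement and a maximum in its justification, and 12 patients support it only as an approximate average per disease. At RHAT rates the chance of reaching 5 in both diseases is about 0.55 under the most favourable split. Investigator discretion can only lower that, and the recruitment clause does not make up a shortfall of one to four continuers.

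The clash in wording rests on no assumption. The probabilities do: they assume the split, full continuation of unresolved patients, and RHAT rates from 5 and 8 patients. They should be read as illustrative. They do not show that the enrolment number, the recruitment clause or any analysis is wrong.

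**What to change.** In the synopsis, Protocol 5.2, Protocol 10.1 and SAP 5.2, keep 5 per disease as the target but restate it. For example:

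*Twelve patients will be enrolled, with a target of about 5 EP and 5 GPP patients continuing beyond Week 12; this is an expected number, assuming roughly equal enrolment by disease, and is not assured.*

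In Protocol 10.1 and SAP 5.2, replace the words that call 5 a maximum with *approximately 5 patients per disease*.

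The enrolment number, the condition for further enrolment and the analyses stay as they are. The cost is a wording change in three places in the protocol and one in the SAP, and a less favourable size statement. The protocol change can wait for the next amendment.

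### The plan states at least 5 continuing patients per disease, but 12 enrolled patients do not assure that, and the only top-up provision applies at zero

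*Protocol*

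**What the plan says.** Protocol 10.1 sets the size: "A total of 12 patients will be enrolled so that at least 5 patients with EP and 5 patients with GPP" are inadequate responders who stay on treatment after Week 12. The next sentence is the only provision for recruiting more: "Additional enrollment may occur and the sample size may be increased, if no GPP or EP patients enter into Period 3". The synopsis, Protocol 5.2 ("Additional enrollment may occur and sample size may be increased, if no GPP or EP patients enter into Period 3") and SAP 5.2 carry the same target and the same trigger. The SAP Version 2 change list (SAP 3) does not mention either.

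Two reasons are given for the size. The first is the earlier study: "In the I1F-JE-RHAT (RHAT) study, 5 GPP and 8 EP patients were enrolled", from which "it is assumed that approximately 5 patients at maximum may not achieve" GIS = 1 at Week 12 and may go on, at the investigators' discretion. The second is practical: "The sample size is determined based on the feasibility in Japan".

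Neither document says how the 12 divide between GPP and EP. The primary endpoint is counted separately for each disease in the patients dosed in Period 3 (Protocol 10.3.3.1, SAP 6.11.1). No inference is planned (Protocol 10.3.1, SAP 6.1).

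**The concern.** The section gives three figures for how many patients continue, and they do not fit together.

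- **Minimum:** 5 per disease, so 10 in all.
- **Assumed maximum:** about 5, with no statement of whether this is per disease or in total. If it is a total, 10 cannot be reached. If it is per disease, the ceiling equals the floor, and the target is met only when both diseases reach their maximum.
- **Trigger for more enrolment:** zero.

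Between zero and five there is no text. A disease with 1, 2, 3 or 4 patients in Period 3 falls below the stated minimum, and nothing says whether recruitment may continue or whether the number is acceptable. It is also not stated whether the trigger needs one disease to be empty or both.

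What is at stake is the size of each per-disease group. The study exists because there were no data in EP and GPP patients on Q2W dosing beyond 12 weeks (Protocol 3.2). In a group of 5, each patient is worth 1/5 = 20 percentage points; in a group of 4, 25 points; in a group of 1, all 100.

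**Working it through.** **Inputs.** N = 12, a target of 5 per disease and a trigger at 0 per disease (Protocol 10.1). For RHAT, the same section reports one of 5 GPP patients resolved "at Week 12 and the other 4 GPP patients achieved" GIS = 2, giving 4/5 = 0.80 not resolved. It reports one of 8 EP patients resolved "at Week 12 and 7 EP patients achieved" GIS = 2, giving 7/8 = 0.875.

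**Assumptions of this review.** The split is 6 GPP and 6 EP, with 5/7 and 7/5 as alternatives. Patients are independent. The RHAT proportions serve as continuation rates. They are upper limits in the sense that GIS ≥ 2 is required to continue and investigator discretion can only remove patients.

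**The plan's figure of 12.** No formula is given, but an expected-count argument reproduces it: 10 / (11/13) = 11.8, rounded up to 12. By disease it is 5/0.80 = 6.25 and 5/0.875 = 5.71, rounded up to 7 + 6 = 13. So 12 gives about the right number on average. At 6/6 the expected counts are 6 × 0.80 = 4.8 GPP and 6 × 0.875 = 5.25 EP.

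**Chance of reaching 5 of 6**, P = 6p⁵(1 − p) + p⁶:

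- GPP: 6 × 0.32768 × 0.2 + 0.26214 = 0.655
- EP: 6 × 0.51291 × 0.125 + 0.44880 = 0.833
- Both: 0.655 × 0.833 = 0.546, so at least one disease is short with probability 0.454

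**Chance that the trigger applies** (either disease empty), where P(0) = (1 − p)⁶:

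- GPP: 0.2⁶ = 0.000064
- EP: 0.125⁶ = 0.0000038
- Either: 0.000068, or 0.007%

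An empty disease is always a miss, so the share of misses in which the trigger applies is 0.000068 / 0.454 = 0.015%, about 1 in 6,700. If the trigger needs both diseases empty, its probability is 0.000064 × 0.0000038 = 2.4 × 10⁻¹⁰.

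**Other splits and rates:**

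| Scenario | At least one disease short | Trigger applies, all trials | Trigger applies, among misses |
|---|---|---|---|
| 6/6, RHAT rates | 45.4% | 0.007% | 0.015% |
| 5 GPP/7 EP, RHAT rates | 68.8% | 0.032% | 0.047% |
| 7 GPP/5 EP, RHAT rates | 56.3% | 0.004% | 0.008% |
| 6/6, common rate 0.9 | 21.6% | 0.0002% | 0.0009% |
| 6/6, common rate 0.6 | 94.6% | 0.8% | 0.9% |
| 6/6, common rate 5/12 | 99.8% | 7.7% | 7.7% |
| 6/6, common rate 0.3 | over 99.9% | 22.1% | 22.1% |
| 6/6, common rate 0.2 | nearly 100% | 45.6% | 45.6% |

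The 5/12 row reads the assumed maximum as 5 patients in total. Reading it as 5 of 6 per disease gives P(5 or more) = (5/6)⁵ × (1 + 5/6) = 0.4019 × 1.8333 = 0.737, and a shortfall of 1 − 0.737² = 46%.

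**The case against.** The strongest reply is that the two sentences have different jobs. The target states what 12 patients are hoped to yield. The top-up provision guards against a disease with no Period 3 data at all, which would leave half of the regulatory commitment unanswered. Read that way they can coexist. This stands: a reader might infer that the provision exists to protect the figure of 5 and therefore contradicts it, but neither document states its purpose. What remains is a gap for 1 to 4 patients.

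A reader might also infer that the provision secures at least one patient per disease. It does not. It is permissive, so it assures no number, and a permissive trigger set at 5 would not assure 5.

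Third, a reader might say that the trigger almost never applies when the target is missed. That holds at the RHAT rates. It weakens if discretion holds many patients back: about 8% of misses at 5 of 12 continuing, 22% at a rate of 0.3 and 46% at 0.2. The protocol's own assumed maximum makes such rates possible.

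Fourth, the shortfall probabilities mainly show whether 12 is enough; they would be the same with no top-up provision. This is correct, and it is why the first remedy is to restate the target.

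Finally, no power or error rate depends on reaching 5, results are counts with by-patient listings (SAP 6.11), and 4 patients inform little less than 5. Feasibility is a stated and reasonable limit. These points lower the severity. They do not explain a stated minimum that the same section's assumed maximum does not support.

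**Conclusion.** The point holds as an unsupported figure and a gap in the text, at low severity. The design does not assure 5 continuing patients per disease. At RHAT rates the chance that at least one disease falls short is about 45% with a 6/6 split, 69% with 5 GPP/7 EP and 56% with 7/5. If 5 of the 12 continue in total, it is near certain. The only top-up provision leaves 1 to 4 patients uncovered, and the assumed maximum of about 5 does not fit a minimum of 5 per disease.

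These sizes rest on an assumed split and on rates from 5 and 8 patients; at a common rate of 0.9 the shortfall would be about 22%. How often the trigger applies depends on investigator discretion, which the documents do not quantify. The documents do not support saying that the provision was written to protect the target, or that it guarantees any number. The effect is on the stated count and the precision of each per-disease result, not on a test.

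**What to change.** In the synopsis, Protocol 5.2, Protocol 10.1 and SAP 5.2:

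1. Restate 5 per disease as a goal limited by feasibility that 12 enrolled patients do not assure.
2. Give the planned split and the expected number continuing per disease, with the continuation rate used. At 6/6 and RHAT rates this would be 4.8 GPP and 5.25 EP before discretion is allowed for.
3. Say whether the assumed maximum of about 5 is per disease or in total, and reconcile it with the goal.
4. State that the top-up provision means either disease, not both.

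This is wording only. Its cost is a less favourable stated figure.

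Optionally, if the sponsor does want 5 as a minimum, let the permissive top-up apply when fewer than 5 patients of either disease enter Period 3. The cost is possible extra recruitment in a rare disease: the provision would be open in about 45% of trials at 6/6 and RHAT rates (69% and 56% at the other splits), and each added patient needs 12 weeks of induction before Period 3 entry is known. For scale, at the RHAT rates 8 GPP patients (94.4%) and 7 EP patients (95.4%), 15 in all, would each give at least a 90% chance of 5 continuing. Whether that is feasible is for the sponsor to judge.
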